6.6 Withdrawal from trial

The subject may withdraw consent at will at any time either by the subject and/or by the subject's LAR. The subject's request to withdraw from the trial must always be respected.

See Section [8.1.9](#) for procedures to be performed for subjects withdrawing consent.

For Mexico only: Should the subject, his/her family members parents or legal representative decide to withdraw the consent for participation in the trial, the subject will be entitled to receive appropriate, free of charge medical care and/or trial drug during the follow up period of the protocol when it will be established with certainty that no untoward medical consequences of the subject's participation in the research occurred.

6.7 Subject replacement

Subjects who discontinue trial product prematurely or withdraw consent will not be replaced.

6.8 Rationale for trial population

In the weight management programme, liraglutide 3.0 mg as an adjunct to a reduced calorie diet along with increased physical activity produced clinically relevant and sustained weight loss in adults with overweight or obesity with or without diabetes. Weight loss with liraglutide 3.0 mg was accompanied by beneficial effects on multiple secondary efficacy parameters (i.e., glycaemia, blood pressure, lipid profile).

As with adults, the prevalence of overweight/obesity has tripled in the adolescent population during the past three decades and current projections predict a further increase^{3,7,39}. Paediatric obesity is associated with a number of complications, including hypertension, T2DM, early puberty, menstrual irregularities, polycystic ovary syndrome, steatohepatitis, sleep apnoea, asthma, musculoskeletal disorders and psychological problems⁷. Furthermore, paediatric overweight/obesity is an independent risk factor for obesity in adulthood⁸, thus predisposing to future comorbid conditions and reduced life expectancy^{10,29}. In the paediatric population, weight loss has been associated with improvements in cardiometabolic risk factors, including measures of glycaemic control, beta-cell function, insulin sensitivity/resistance, lipid profile, systolic/diastolic blood pressure and metabolic syndrome¹¹⁻¹⁴.

No safety/tolerability concerns for adolescents with obesity aged 12–17 years were raised in the 5-6 week NN8022-3967 trial investigating the safety/tolerability and pharmacokinetics of liraglutide doses up to 3.0 mg. Data from the NN8022-3967 trial, as well as the PK modelling analysis based on this trial, have resulted in the decision to use a starting dose of 0.6 mg in the current trial. The present trial will investigate the efficacy and safety of liraglutide for weight management in the same subject population.

7 Milestones

Planned duration of recruitment period is 52 weeks from global first patient first visit (FPFV).

End of trial is defined as last patient last visit (LPLV).

Recruitment:

A global recruitment strategy will be developed in cooperation with the participating countries to ensure that a sufficient number of subjects are randomised. Prior to FPFV, all sites should have a site-specific recruitment strategy in place detailing how many subjects they can recruit within a certain period.

The screening and randomisation rate will be followed closely via IWRS in order to estimate when to stop screening. All investigators will be notified immediately when the recruitment period ends, after which no further subjects may be screened and the IWRS will be closed for further screening. All subjects screened during the recruitment period and found eligible for randomisation can be randomised within the timelines specified in the flowchart (see Section [2](#)).

Trial registration:

Information of the trial will be disclosed at clinicaltrials.gov and novonordisk-trials.com. According to the Novo Nordisk Code of Conduct for Clinical Trial Disclosure⁴⁰, it will also be disclosed according to other applicable requirements such as those of the International Committee of Medical Journal Editors (ICMJE)⁴¹, the Food and Drug Administration Amendment Act (FDAAA)⁴², European Commission Requirements⁴³⁻⁴⁵ and other relevant recommendations or regulations. If a subject requests to be included in the trial via the Novo Nordisk e-mail contact at these web sites, Novo Nordisk may disclose the investigator's contact details to the subject. As a result of increasing requirements for transparency, some countries require public disclosure of investigator names and their affiliations.

8 Methods and assessments

The following Sections describe the assessments and procedures that must be performed during this trial. The overview of when they must be performed is included in the flowchart (see Section [2](#)).

8.1 Visit procedures

It is the responsibility of the investigator to ensure that all site visits and phone contacts occur according to the flowchart. In order to secure consistency in data over time it is encouraged that assessments are performed consistently (e.g., using the same equipment and site staff with alike qualifications) throughout the trial.

All trial procedures must be performed as described in the protocol. Any discrepancies will result in protocol deviations and appropriate actions must be taken to avoid recurrence of the detected discrepancies.

The investigator must keep a subject screening log, a subject identification code list and a subject enrolment log. Only subjects who have signed the informed consent form should be included on the logs. The subject screening log and subject enrolment log may be combined in o

8.1.1 Information visit, visit 1

Informed assent and informed consent from the subject's LAR(s) must be obtained before any trial-related activity; see Section [18.2](#). All subjects and subject's LAR(s) must be provided with a copy of their own signed and dated informed assent form and informed consent form.

A screening session must be made in the IWRS. Each subject will be assigned a unique 6-digit subject number which will remain the same throughout the trial.

All subjects must be reminded to attend the screening visit in a fasting state. Screening must take place at least 1 day after the information.

8.1.2 Fasting

The subjects must attend some visits fasting; see Section 2. Fasting is defined as having consumed no food or drink except for water for the last 8 hours before blood sampling. For V26 and V28, only 2 hours fasting (i.e. no food or drink except for water) is needed before blood sampling for anti-liraglutide antibodies and liraglutide plasma concentrations.

Any prescribed medication which should be taken with or after a meal should be withheld on the day of the visits attended fasting, until blood sampling and body weight measurements have been performed. Trial product can be taken as usual in relation to visits attended fasting except V14, V15, V16, V19, V22, and V25; see Section [8.6.1](#).

In case a subject attends a fasting visit in a non-fasting state, all non-fasting measurements should be performed. The subject should return to the site in a fasting state to have fasting measurements done within the visit window for the relevant visit.

8.1.3 Screening visit, visit 2

At screening, subjects will be provided with a card stating that they are participating in a trial and giving contact address(es) and telephone number(s) of relevant trial site staff. Subjects should be instructed to return the card to the investigator at the last trial visit or to destroy the card after the last visit.

All screening assessments as described in Section [2](#) must be performed and data recorded in the eCRF. For screening failures, please refer to Section [8.1.5](#).

8.1.4 Run-in visits

Subject's eligibility according to the in- and exclusion criteria must be evaluated before the 12-week run-in period is initiated.

V4 and V6 can be performed as phone visits. All subjects must be reminded to attend V8 and the randomisation visit in a fasting state.

During the run-in period the investigator should evaluate the subject's compliance with the run-in procedures and visit schedule. If deemed acceptable, as judged by the investigator, the subject can proceed to randomisation visit. If not, the subject is a screening failure ([8.1.5](#)).

All run-in assessments as described in Section [2](#) must be performed and data recorded in the eCRF. For screening failures, please refer to Section [8.1.5](#).

8.1.5 Screening failures

A screening failure is a subject who does not fulfil one or more of the inclusion and/or exclusion and/or randomisation criteria. For screening failures the screening failure form in the electronic case report form (eCRF) must be completed with the reason for not continuing in the trial. Serious adverse events (SAE) from screening failures must be transcribed by the investigator into the eCRF. Follow-up on SAEs must be carried out according to Section [12](#). A screening failure session must be made in the IWRS. The case book must be signed.

8.1.6 Re-screening

Re-screening is NOT allowed if the subject has failed one of the inclusion, exclusion criteria or randomisation criteria, this includes re-sampling if the subject has failed one of the exclusion criteria related to laboratory parameters.

8.1.7 Randomisation and initial trial product dose

Subjects' eligibility according to the randomisation criteria must be evaluated before randomisation. To randomise a subject, a randomisation session must be performed in IWRS. Tanner stage, HbA_{1c} and FPG status from V8 must be entered in IWRS; see Section [11](#).

All subjects must be instructed in handling of the device and the trial product; see Section [9](#). This should include training in injection site (see Section [5.3](#)) and injection technique. Subjects should be instructed to perform an air shot before the use of a new pre-filled pen. At all subsequent visits, subjects should be re-trained at the investigator's discretion.

The initial dose of trial product must be injected by the subject or the subject's LAR at the site and this must be documented in the subject's medical record. The initial dose of trial product must be injected post blood sampling.

For training in symptom recognition and handling of hypoglycaemia; see Section [8.4.13](#). For instruction in handling of the BG meter including auxiliary supplies and self-measured plasma glucose (SMPG); see Section [8.4.2](#).

8.1.8 Dose escalation

Treatment with trial product will be initiated at randomisation with 0.6 mg daily for one week and increased in weekly steps of 0.6 mg until MTD or the 3.0 mg dose of trial product (highest allowed dose) is reached. Ideally, subjects will reach maximum dose of 3.0 mg at V13.

The SMPG measurement performed during dose escalation visits (Section [8.4.2](#)) must be performed before instructing the subject in dose escalation.

8.1.8.1 Dose escalation and tolerability

Dose escalation is based on tolerability as judged by the investigator.

The trial product dose escalation should continue to next dose level only if the present dose is tolerated. If, after increasing to next dose level, the dose is poorly tolerated, it is allowed to be lowered to the previously dose level.

If a subject has tolerability issues with a given dose level, it is allowed to remain at that dose level for a maximum of 2 weeks. This extended time of one additional week is allowed at each dose level (i.e., the dose escalation process may take up to 8 weeks in total). It is at the discretion of the investigators to judge when the subject has reached MTD.

Escalation of the trial product is not allowed if the subject has a self-measured plasma glucose (SMPG) < 3.1 mmol/L (56 mg/dL) or < 3.9 mmol/L (70 mg/dL) in the presence of symptoms of hypoglycaemia during the week prior to or during the dose escalation visits, or during contacts (i.e.,

via telephone). Hypoglycaemic episodes must be reported in the eCRF according to Section [8.4.2](#), [8.4.13](#), [8.5.3](#) and [12.1.1](#).

Visits to the clinic occur weekly during the first 4 weeks of dose escalation at V10-V13. Ideally, subjects will reach maximum dose of 3.0 mg at V13.

In those cases where more than one week is needed at any dose escalation step, the subject must still follow the visit schedule (V10-V13). For the remaining dose escalation step(s) after V13, is it at the discretion of the investigator to be in frequent contact (e.g., by phone) with the subject to ensure correct dose settings. The dose escalation process must be finalised no later than V14.

Contacts regarding dose escalation must be documented in the subject's medical record.

8.1.8.2 Tolerability at maximum tolerated dose

In case a subject experiences tolerability issues at the MTD during the trial, as judged by the investigator, the trial product dose may be lowered to the next, lower dose level as needed: from 3.0 mg to 2.4 mg, from 2.4 mg to 1.8 mg, from 1.8 mg to 1.2 mg, and from 1.2 mg to 0.6 mg.

The reason for lowering the trial product dose must be documented in the subject's medical record.

If the cause of the subject's tolerability issues is intermittent illness or otherwise transient, as judged by the investigator, the subject is allowed to return to MTD again.

If a subject treated with 0.6 mg experiences persistent intolerance, as judged by the investigator, the trial product must be discontinued.

8.1.8.3 Recording of trial product dose levels in eCRF

The investigator must record the trial product dose, date of dose level changes and reason for changes in the eCRF throughout the trial.

8.1.9 Withdrawal from trial

If a subject and/or the subject's LAR(s) withdraw consent, the investigator must aim to undertake procedures similar to those for the end of treatment (V25) as soon as possible, and a follow-up visit (V26) two weeks later.

If a subject and/or the subjects LAR(s) withdraw consent after end of treatment (V25), the investigator must aim to undertake procedures similar to those for the end of trial (V30) as soon as possible.

The end of trial form must be completed and final drug accountability must be performed even if the subject is not able to come to the trial site. A treatment discontinuation session must be made in IWRS. The case book must be signed.

Although a subject is not obliged to give his/her reason(s) for withdrawing consent, the investigator must make a reasonable effort to ascertain the reason(s), while fully respecting the subject's rights. Where the reasons are obtained, the primary reason for withdrawing consent must be specified on the end-of-trial form in the eCRF.

8.1.10 Premature discontinuation of trial product

If a subject prematurely discontinues trial product, the investigator must aim to undertake procedures similar to those for the end of treatment (V25) as soon as possible, and a follow-up visit (V26) two weeks later.

The subjects must be asked to attend additional visits depending on when the trial product discontinuation takes place during the trial:

- If the trial product is discontinued before V19 subjects must be asked to attend three additional visits (V19x, V25x and V30x) taking place weeks 30, 56 and 82 after randomisation, respectively.
- If the trial product is discontinued after V19 and before V25 subjects must be asked to attend two additional visits (V25x and V30x) taking place weeks 56 and 82 after randomisation, respectively.

The primary reason for premature discontinuation of trial product must be specified on the end of trial form in the eCRF, and final drug accountability must be performed. A treatment discontinuation session must be made in the IWRS.

8.2 Subject related information/assessments

8.2.1 Demography

Demography will be recorded at screening and consists of:

- Date of birth (according to local regulation)
- Sex
- Ethnicity (according to local regulation)
- Race (according to local regulation)

8.2.2 Concomitant illness and medical history

A **concomitant illness** is any illness that is present at the start of the trial (screening visit) or found as a result of a screening procedure or other trial procedures performed before exposure to trial product. All concomitant illnesses should be reported.

Any change to a concomitant illness should be recorded during the trial. A clinically significant worsening of a concomitant illness must be reported as AEs.

Medical history is a medical event that the subject has experienced in the past. Only relevant and significant medical history, as judged by the investigator, should be reported. Following medical history should be reported as a minimum if applicable: diagnose of T2DM, cardiovascular diseases, gallstone diseases (e.g., cholecystitis), pancreatitis and psychiatric disorders.

The information collected for concomitant illness and medical history should include diagnosis, date of onset and date of resolution or continuation, as applicable.

It must be possible to verify the subject's medical history in source documents such as subject's medical record. If a subject is not from the investigators own practice; the investigator must make reasonable effort to obtain a copy of subject's medical record from relevant party e.g. primary physician. The investigator must document any attempt to obtain external medical information by noting the date(s) when information was requested and who has been contacted.

8.2.2.1 History of psychiatric disorders

Information related to psychiatric disorders (specifically history of depression, suicidal behaviour, anxiety, mood disorders, insomnia or sleep disorders) must in addition to the medical history form also be recorded in the eCRF on a separate form.

8.2.3 Concomitant medication

A **concomitant medication** is any medication, other than the trial product, which is taken during the trial, including the screening, run-in and follow-up periods.

Details of any concomitant medication must be recorded at screening. Changes in concomitant medication must be recorded at each visit as they occur.

The information collected for each concomitant medication includes trade name or generic name, indication, start date and stop date or continuation. In addition, dose and route of administration for concomitant medication treatment for weight-related co-morbidities (diabetes, hypertension and dyslipidaemia) must be recorded.

If a change is due to an AE, then this must be reported according to Section [12](#). If the change influences the subject's eligibility to continue in the trial, the monitor must be informed.

8.2.4 Childbearing potential

It must be recorded in the eCRF whether female subjects are of child-bearing potential.

Female subjects of child-bearing potential must be instructed to use adequate contraceptive methods throughout the trial and until 1 week after end of treatment.

Pregnancy testing must be performed on female subjects of child bearing potential (females who have had their first menstrual period) as described in Sections [8.2.4.1](#) and [8.2.4.2](#).

8.2.4.1 Blood sample for pregnancy testing

At screening and/or V25, a serum pregnancy test must be performed.

If a female subject becomes of child-bearing potential during the trial, a serum pregnancy test must be performed as soon as possible or at the latest at the next clinic visit.

8.2.4.2 Urine-sticks pregnancy testing

Urine-stick pregnancy tests will be performed at the site during the trial if pregnancy is suspected, if a menstrual period is missed (unless this is a part of the mode of action of the contraceptive method) or if in accordance with local requirements.

Documentation of result of urine-stick pregnancy test must be recorded in the eCRF.

8.2.5 Tobacco use

Details of tobacco use must be recorded according to Section [2](#). Smoking is defined as smoking at least one cigarette or equivalent daily.

Smoking status:

- Never smoked
- Previous smoker, smoking stop date
- Current smoker

8.3 Efficacy assessments

The timing of the assessments is outlined in the flowchart; see Section [2](#). The assessments performed at randomisation are the baseline measurement, unless otherwise specified.

8.3.1 Body measurements

8.3.1.1 Body weight

Body weight must be measured to the nearest 0.1 kg or 0.1 pounds. Fasting body weight must be measured at the fasting visits (Section [8.1.2](#)). If the weight is not measured fasting at fasting visits, the subject must be called in for a new visit within the visit window to have the fasting weight measured. At the remaining visits, the measurement is performed in a non-fasting state.

The same digital scale should be used throughout the trial. The scale must be calibrated according to the directions for use and, as a minimum, once a year.

Weight should be measured without shoes and only wearing light clothing and the subject should have an empty bladder.

Weight measured at screening is used for the calculation of BMI, whereas weight measured at randomisation is used as baseline for assessment of change in body weight. BMI is calculated in the eCRF.

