4.2 Endpoints

4.2.1 Primary endpoint

Change in body mass index (BMI) standard deviation score (SDS) from baseline (randomisation) to 56 weeks³³.

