5.3 Treatment of subjects

Subjects will undergo a 12-week run-in period during which they will receive counselling in healthy nutrition and physical activity. This counselling will continue throughout the 56-week blinded period and the 26-week off-study-drug follow-up period.

Subjects who are eligible for randomisation will be administered liraglutide or placebo by a once-daily s.c. injections. Placebo contains the same excipients as liraglutide, but no active drug substance. Subjects randomised to receive placebo will receive s.c. injections with injection volumes corresponding to the liraglutide dose.

The injections can be done either in the abdomen, thigh, or upper arm. Injection region consistency is not required throughout the trial.

Injections can be administered at any time of day irrespective of meals. It is recommended that the time of injection for a subject is consistent throughout the trial.

Based on the results of the NN8022-3967 PK trial in pubertal adolescents with obesity (aged 12-17 years), including model-estimated steady-state exposure, treatment with liraglutide will be initiated with 0.6 mg daily for one week and increased in weekly steps of 0.6 mg until a maximum tolerated dose (MTD) or the 3.0 mg dose of liraglutide (highest allowed liraglutide dose) is reached. Dose escalation will be based on tolerability as judged by the investigator and the duration will be from 4-8 weeks (see Section [8.1.8.1](#)).

Subjects and their legally acceptable representative (LAR) will be instructed in symptom recognition and handling of hypoglycaemia, and in blood glucose measurements at randomisation (see Section [8.4.13](#)).

Medications that should not be used within 90 days before screening and during the trial are listed in Sections [6.3](#) and [6.5](#).

Subjects who at screening have a diagnose of T2DM can enter the trial. The only allowed anti-diabetic treatment is metformin.

If a subject develops T2DM ([Table 5–1](#)) during the course of the trial, he/she will be allowed to remain on trial product if glycaemic control can be achieved through healthy nutrition and physical activity, according to local standard of care. Furthermore, additional treatment with metformin is allowed, at the discretion of the investigator.

If diabetes treatment other than healthy nutrition, physical activity and metformin is required for glycaemic control, the trial product must be discontinued (see Sections [6.5](#) and [8.1.10](#)).

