Lifestyle modification is the recommended first-line treatment for overweight/obesity in the paediatric population^{[15,16](#)}. Therefore a 12-week run-in period with structured counselling in healthy nutrition and physical activity is included in the trial. Only subjects who, after this lifestyle modification attempt, still fulfil the definition of obesity can be randomised (as defined by inclusion

Protocol
Trial ID: NN8022-4180
UTN: U1111-1162-7101
EudraCT no.: 2014-004353-14

~~CONFIDENTIAL~~

Date: 01 June 2016
Version: 1.0
Status: Final
Page: 30 of 110

Novo Nordisk

and randomisation criteria). Currently, no pharmacologic agents are approved for weight management in the paediatric population with obesity in the European Union. Although orlistat has FDA approval for the above-mentioned indication in adolescents aged ≥ 12 years, its weight loss efficacy is modest and treatment compliance is low due to gastrointestinal adverse effects¹⁷⁻¹⁹. Therefore, a placebo comparator group will be used to evaluate whether liraglutide, in combination with healthy nutrition and physical activity, is more efficacious for the treatment of obesity than healthy nutrition and physical activity alone.

6 Trial population

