6.4 Randomisation criteria

To be randomised, all randomisation criteria must be answered "yes".

1. BMI corresponding to ≥ 30 kg/m² for adults by international cut-off points and \geq the 95th percentile for age and sex (for diagnosis of obesity).
2. Compliance with run-in procedures and visit schedule as judged by the investigator.
3. PHQ-9 score < 15 at randomisation
4. No suicidal ideation of type 4 or 5 since last visit based on the C-SSRS questionnaire at randomisation

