8.6.2 Counselling in healthy nutrition and physical activity

8.6.2.1 Counselling in healthy nutrition

Subjects (and subjects' LAR, as applicable) must receive individualised counselling in healthy nutrition with the goal of obtaining a weight loss. The counselling must be performed by a certified dietitian according to local standard. The focus of the counselling in healthy nutrition must be facilitating healthier food choices.

If a BMI corresponding to $\leq 25 \text{ kg/m}^2$ for adults by international cut-off point⁵³ is reached, subjects should be assigned a maintenance diet, at the discretion of the investigator. For details, refer to Appendix A.

Counselling in healthy nutrition can be done by phone and must be documented in subject's medical record.

Healthy nutrition compliance must be evaluated at every visit by the dietitian, using a numerical rating scale (NRS), and the results must be provided to the investigator. The investigator or delegated staff must record the NRS into the eCRF.

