When visit windows are used, all visits will be re-aligned, i.e., they will be mapped into one of the visit windows. For example, if the Week 4 visit of a subject is delayed and occurs on Day 46 instead of on Day 29, it will be re-aligned to visit window Week 8. In the case of major deviations from the visit schedule, or due to unscheduled visits, several assessments of a subject may fall in a particular visit window (either scheduled or unscheduled). Statistical approaches to handle multiple assessments in a given visit window are specified below.

In general, if two consecutive visits V_t and V_s are x days apart, the upper limit of the visit window for V_t will be $V_t+x/2$ and the lower limit for the visit V_s will be $V_s-x/2$ (if x is even, the lower limit for V_s will be $V_s-x/2+1$, and the upper limit for V_t will be $V_t+x/2$). The algorithm needs to ensure that visit windows are not overlapping and that there are no gaps, such that each assessment can be uniquely allocated to one visit window, e.g., if Week 8 visit is scheduled for day 57, Week 12 is scheduled at Day 85 and Week 16 is scheduled at Day 113, then the visit window for week 12 extends from Day 72 to Day 99.

Note: The lower limit of first visit will be assigned with -999 which accommodate all assessments occurred before the scheduled day.

The upper limit of last visit will be assigned with 999 which accommodate all assessments occurred after the scheduled day.

Table 3-1: Assessment windows for scheduled visits

Analysis Visit	Week	Scheduled Day	Visit Window
Visit 2 (screening)	week -14	-98	Day -999 to -91
Visit 3 (week -12)	week -12	-84	Day -90 to -70
Visit 5 (week -8)	week -8	-56	Day -69 to -42
Visit 7 (week -4)	week -4	-28	Day -41 to -21
Visit 8 (week -2)	week -2	-14	Day -20 to -7
Visit 9 (week 0)	Randomisation	1	Day -6 to 4
Visit 10 (week 1)	week 1	8	Day 5 to 11
Visit 11 (week 2)	week 2	15	Day 12 to 18
Visit 12 (week 3)	week 3	22	Day 19 to 25
Visit 13 (week 4)	week 4	29	Day 26 to 43
Visit 14 (week 8)	week 8	57	Day 44 to 71
Visit 15 (week 12)	week 12	85	Day 72 to 99
Visit 16 (week 16)	week 16	113	Day 100 to 127
Visit 17 (week 20)	week 20	141	Day 128 to 158
Visit 18 (week 25)	week 25	176	Day 159 to 193
Visit 19 (week 30)	week 30	211	Day 194 to 225
Visit 19x (week 30 follow-up)	week 30	211	Day 194 to 225
Visit 20 (week 34)	week 34	239	Day 226 to 253
Visit 21 (week 38)	week 38	267	Day 254 to 281
Visit 22 (week 42)	week 42	295	Day 282 to 309

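### Protocol 8.3.1.1 ties the BMI calculation to the screening weight without limit, so the obesity check at randomisation could be run on a pre-run-in weight

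*Protocol*

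**What the plan says.** Protocol 8.3.1.1 gives the two weights two uses: "Weight measured at screening is used for the calculation of BMI, whereas weight measured at randomisation is used as baseline" for change in body weight. It then says that BMI is calculated in the eCRF. It names no visit to which the BMI half of the sentence is confined.

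Other sections bear on the same BMI:

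- Protocol 5.3: "Subjects will undergo a 12-week run-in period during which they will receive counselling in healthy nutrition and physical activity". Under 8.6.2.1 this is "individualised counselling in healthy nutrition with the goal of obtaining a weight loss". Screening (V2) is at week -14, before the run-in starts.
- Protocol 5.5: "Only subjects who, after this lifestyle modification attempt, still fulfil the definition of obesity can be randomised".
- Protocol 6.4: "To be randomised, all randomisation criteria must be answered" yes. Criterion 1 repeats the BMI test of inclusion criterion 3. Section 8.1.7 has these criteria evaluated before randomisation, and Appendix A applies its cut-off tables to 6.4 as well as 6.2.
- Protocol 4.2.1: the primary endpoint is the change in BMI "standard deviation score (SDS) from baseline (randomisation) to 56 weeks".
- Protocol 8.3: "The assessments performed at randomisation are the baseline measurement, unless otherwise specified".
- Protocol 17 and SAP 2 take baseline as the most recent available of the V9 and V8 values, also with an exception clause. SAP 2.3.1 uses the randomisation value, and the screening value if that one is missing.

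**The concern.** Criterion 1 in 6.4 exists because the run-in may work. A subject who has lost enough weight on lifestyle counselling alone is meant to stop there. If the eCRF computes the V9 BMI from the screening weight, the repeat test contains no new weight and cannot identify that subject.

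The decision is taken at the site, before any rule in the SAP applies, so no analysis convention can repair it. It also has consequences inside the protocol. Section 8.1.6 does not allow re-screening after a failed randomisation criterion, and 6.5 item 2 requires trial product to be stopped in a subject included in violation of one. Whether a subject near the cut-off is correctly randomised, a screening failure or a violation can therefore depend on which sentence the site follows.

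A second, weaker tension is with 4.2.1. A BMI built on the week -14 weight is not a randomisation value. If it were carried into the analysis as baseline, weight lost in the run-in would be counted as change under treatment.

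**Working it through.** **1. What each passage implies at V9.**

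| Source | Weight implied for BMI at V9 |
|---|---|
| Protocol 8.3.1.1, as written | Screening, week -14 |
| Protocol 5.5 | After the run-in |
| Protocol 6.4 with 8.1.7 | Not named; checked before randomisation |
| Protocol 4.2.1 (baseline) | Randomisation |

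In 6.4, criteria 3 and 4 (PHQ-9 and C-SSRS) say that they are assessed at randomisation. Criterion 1 does not, so 6.4 alone does not resolve the conflict.

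**2. Eligibility example.** The subject is hypothetical: a boy aged 15.0 at V9, with height 1.70 m assumed unchanged since V2. Appendix A Table 1 gives a cut-off of 28.30 kg/m². The 95th percentile in Table 4 is 25.2, so the international cut-off is the binding one.

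- Weight at the cut-off: 28.30 × 1.70² = 28.30 × 2.89 = 81.8 kg
- Screening weight 84.0 kg: 84.0 / 2.89 = 29.07, passes
- V9 weight 81.0 kg: 81.0 / 2.89 = 28.03, fails

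The two readings give opposite answers. More generally, a weight change of k kg moves BMI by k / height². For 1 to 5 kg at heights of 1.60 to 1.70 m (assumed), that is 1/1.70² = 0.35 to 5/1.60² = 1.95 kg/m².

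**3. Responder endpoints, only if a screening-weight BMI is carried through as baseline.** Let r be the fractional BMI loss in the run-in (assumed; the documents give no figure). The further loss after randomisation that would count as a 5% response is 1 − 0.95/(1 − r); for 10% it is 1 − 0.90/(1 − r).

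| r | Further loss for 5% | Further loss for 10% |
|---|---|---|
| 1% | 4.04% | 9.09% |
| 2% | 3.06% | 8.16% |
| 3% | 2.06% | 7.22% |

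**4. Sample size.** The planned figure reproduces without reference to this issue. The inputs from Protocol 17.1 are a difference of 0.26, an SD of 0.35, 40% withdrawal, two-sided 5% and 90% power.

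- Diluted difference: 0.26 × 0.60 = 0.156
- Average variance: 0.35² + ½ × 0.4 × 0.6 × 0.26² = 0.1225 + 0.0081 = 0.1306, so SD 0.3614
- Noncentral t calculation: 114 per arm, 228 in total, as stated

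Correcting the wording leaves these inputs as they are.

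**The case against.** The strongest reply is that the sentence cannot mean what it literally says. If every BMI used the screening weight, BMI could change only through height, and the week 30, 56 and 82 endpoints would be empty. It must have been written for the V2 inclusion check, and 5.5 is explicit about persistence of obesity after the run-in. This is very likely the intent. It explains the wording but does not correct it, because the V9 check is the other place where a site needs a BMI for eligibility. The next subsection but one, 8.3.2, ties its three-measurement mean to screening and to eligibility, so the protocol limits such a rule elsewhere and does not do so here.

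A reader might go further and infer that the primary endpoint and the responder endpoints run from a week -14 baseline, so that run-in loss is credited to liraglutide. The documents do not support that:

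- The sentence names no baseline for BMI. Where the protocol moves a baseline it says so, as for the ECG (8.4.4) and glucose metabolism (8.5.3).
- Section 4.2.1, Protocol 17, SAP 2 and SAP 2.3.1 all put baseline at randomisation, or at V8, when a value exists there.
- SAP 2.5.1 computes BMI SDS from a measurement at a given age, and SAP 3.4.1.3 treats BMI and BMI SDS as related to the weight and height of the visit.
- Even with carry-through, run-in change precedes randomisation and falls on both arms, so the difference in mean change is not biased.

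Setting a run-in shift in BMI SDS against the planned -0.26 would also mislead. The worked example in SAP 2.5.1 is an 11-year-old, outside the trial's age range, and the comparison would put a within-arm shift beside a between-arm difference.

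**Conclusion.** The conflict is real and concerns eligibility. As written, 8.3.1.1 can give the wrong answer for randomisation criterion 1 in a subject near the cut-off who loses weight during the run-in. The baseline question is secondary: 4.2.1, Protocol 17 and SAP 2.3.1 largely settle it, and the figures in step 3 apply only if a screening-weight BMI from the eCRF is carried through. The randomised mean difference and the 228 subjects are unaffected. Severity is moderate; this is not a defect in the primary analysis.

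The conclusion rests on the text alone. The eCRF derivation is not in the documents, so whether the wrong weight would in fact be used is unknown. The heights, weights and run-in losses are illustrative, and nothing in the documents says how many subjects would cross the cut-off.

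One loose end remains in the baseline rules. If the V9 value is missing, Protocol 17 and SAP 2 fall back to V8, but SAP 2.3.1 falls back to screening. That is the one route by which the SAP itself could admit a week -14 BMI as baseline.

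**What to change.** Reconcile 8.3.1.1 with 5.5, 6.4 and 4.2.1:

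- Limit the screening-weight sentence to the BMI used for inclusion criterion 3 at V2.
- State that BMI at randomisation, for criterion 1 and as baseline, and at later visits uses that visit's weight and height. Say which height applies at visits where none is taken, since SAP Table 3-2 shows that height is not collected at every visit.
- Check that the eCRF derives BMI this way.
- Give one fallback for a missing V9 value in Protocol 17, SAP 2 and SAP 2.3.1.

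The cost is a few sentences and a check of the eCRF specification. No new measurement appears to be needed: 8.3.1.1 already relies on a randomisation weight, and SAP Table 3-2 lists height at V9. Subjects who no longer meet the obesity definition at V9 would become screening failures, as 5.5 intends. If subjects have already been randomised, a listing of V9 BMI against the Appendix A cut-offs would show whether the ambiguity had any effect.
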